## 2 DOSE ESCALATION PROCESS AND SIMULATIONS IN MONOTHERAPY

### 2.1 Dose Escalation Process

Dose escalation recommendations for BMS-986277 monotherapy will be based on the inference from the Bayesian posterior and the probability that the true DLT rate for each dose lies in 1 of the following categories:

- [0%, 16%) under-dosing
- [16%, 33%) targeted toxicity
- [33%, 100%] excessive toxicity

Note: “[” or “[” is inclusive of the respective endpoint, and “(” or “)” exclusive of the respective endpoint.

These boundaries are similar to the toxicity boundaries used by a rule-based design (ie, 3 + 3 design) in that a minimum is set at 16% (~ 1 in 6) DLT rate and a maximum at 33% (~ 2 in 6) DLT

rate. Following the principle of EWOC, dose recommendations for the next cohort will be based on the Bayesian model after DLT information becomes available during the DLT period, accounting for all of the available data from the administered doses, and the candidate doses for the next cohort are the ones fulfilling the overdose criterion that there is no greater than 35% chance of excessive toxicity. Only the candidate doses will be considered for the next cohort. While the Bayesian model will use DLT information from the DLT period only, clinical assessment will take into consideration the totality of available data including PK/pharmacodynamics from all treated participants.

### **Stopping Rules:**

The following are the general stopping rules of BLRM during monotherapy dose escalation:

- If all of 24 DLT-evaluable participants are treated.
- If all of the current prespecified doses are considered intolerable according to the prespecified cutoff (ie, EWOC criteria), then the model will recommend stopping the current dose level and a new dose level lower than the current lowest dose level can be identified.
- The maximum number of DLT-evaluable participants in a dose level will be 12. This limit is set to avoid instances in which the model could recommend adding subjects indefinitely to a specific dose level due to uncertainty in the tolerability profile.
- If, for a specific dose level, 6 subjects have been treated and the chance of determining that the dose level to be the “target” dose is  $> 50\%$ , then the model will suggest to stop and declare the current dose level to be the BLRM-recommended dose (BLRM-RD).

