## **10 STATISTICAL CONSIDERATIONS**

### **10.1 Sample Size Determination**

#### **10.1.1 Dose Escalation**

##### **10.1.1.1 Monotherapy Dose Escalation (Part 1)**

Dose escalation during the BMS-986277 monotherapy dose escalation (Part 1) will be guided by BLRM employing the Escalation With Overdose Control (EWOC) principle. The BLRM method is fully adaptive, makes use of all the information available at the time of each dose assignment, not just data from the current dose level, and directly addresses the ethical need to control the probability of overdosing. Furthermore, the BLRM uses the knowledge gained from participants treated with enadenotucirev. The targeted toxicity rate in this study is in the range of [16%, 33%]. The boundary is similar to the toxicity boundary used by a rule-based design (ie, 3 + 3 design) in that a minimum is set to 16% (approximately 1 in 6) DLT rate and a maximum at 33% (approximately 2 in 6) DLT rate. The use of the EWOC principle limits the risk of exposing participants in the next cohort to an intolerable dose by ensuring the posterior probability of the DLT rate exceeding 33% at any dose is capped at 35%.

Due to the nature of the dose escalation process, the exact number of participants to be treated at each dose level cannot be precisely determined. The maximum number of participants to be treated is approximately 24. However, simulation studies with various scenarios show that the expected number of DLT-evaluable participants is no more than approximately 18 ([Appendix 9](#)). Additional participants (up to a total of 12) may be treated at any dose level to further evaluate the safety, PK, and/or pharmacodynamics profile. The total sample size is up to 72.

Approximately 3 participants will be treated at the starting dose levels of BMS-986277. While the BLRM will use DLT information from the DLT period only, clinical assessment will take into consideration the totality of available data, including PK/pharmacodynamics from all treated participants in assigning a dose level for the next cohort of 3 participants. At least 6 DLT-evaluable participants will be treated at a dose level before it can be recommended as the BLRM-RD for BMS-986277 monotherapy.

The BLRM-RD for BMS-986277 monotherapy is the dose that satisfies the following 3 conditions:

- 1) The empirical posterior probability that the “DLT rate of 16% to < 33%” is greater than a pre-specified value (ie, 50%);

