### **BLRM-RD:**

The BLRM-RD is the dose that satisfies the following 3 conditions:

- 1) The empirical posterior probability that the ‘DLT rate of 16% to  $< 33\%$ ’ is greater than 50%,
- 2) This probability needs to be the largest among the dose levels that satisfy the EWOC condition (ie, the probability that ‘DLT rate  $\geq 33\%$ ’ must be no greater than 35%);
- 3) Minimum number of participants (ie, 6), were treated at this dose level.

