### **Final Recommended Dose:**

The final recommended dose will be based on the BLRM-RD and overall clinical assessment of all available safety, PK/pharmacodynamic, and efficacy data. Lower doses of BMS-986277 may be tested if none of the planned doses are found to be tolerable. Such decisions will be made after discussion and agreement between the investigators and the BMS Medical Monitor.

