## **2.2 Simulation Parameters**

Simulation study was done for monotherapy dose escalation using various hypothetical scenarios. One thousand trial simulations were used for each scenario. All simulations were run using EAST 6.3.1® software BLRM module for BMS-986277 monotherapy. The number of participants to be

treated in each cohort in a specific dose level, the stopping rules used to identify the BLRM-RD, and other simulation parameters are defined as:

- Fixed cohort size: 3
- Probability of overdosing:  $\leq 35\%$
- Target probability of toxicity: 0.33, the upper boundary of the targeted toxicity interval
- Probability of achieving the target toxicity:  $> 50\%$
- Maximum number of participants treated: 24
- Prior specification on model parameters:
  - Mean:  $\log(\alpha_1) = -0.959$ ,  $\log(\beta_1) = 0.884$
  - Variance:  $\log(\alpha_1) = 1.010$ ,  $\log(\beta_1) = 1.537$
  - Correlation: 0.055
- Posterior sampling method: Metropolis Hastings
- Minimum number of participants treated at a given dose level in order to identify the BLRM-RD: 6
- Maximum number of participants at a dose: 12

The provisional dose levels for BMS-986277 monotherapy are  $3 \times 10^{10}$ ,  $3 \times 10^{11}$ ,  $1 \times 10^{12}$ , and  $3 \times 10^{12}$  vp, with  $3 \times 10^{12}$  as the reference dose (dose expected to have 30% DLT).

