### Interpretation and Use of [Figure 2](#):

[figure not shown]
Figure 2 is a snapshot of stacking histogram with DLT information available at dose level  $3 \times 10^{10}$  vp and  $3 \times 10^{11}$  vp. This figure will be updated each time new DLT information becomes available.

When recommending the next dose level, the model will first exclude doses that are intolerable (with overdosing probabilities > 35%, the rate that has been specified for BMS-986277). Among those qualified candidate doses that are considered “tolerable”, the model will select the dose that maximizes the probability of being within the target toxicity range (DLT rate between 16% and 33%). However, there will be no dose skipping during the dose escalation monotherapy phase of the study.

As illustrated in Figure 2, the distribution of predicted DLT rates will be characterized into possibilities falling into 3 different categories. First, dose levels  $3 \times 10^{12}$  vp for BMS-986277 are excluded according to the higher-than-cutoff overdosing probabilities (0.579 for  $3 \times 10^{12}$  vp). Among the remainder of tolerable dose levels, the BLRM recommends the dose that maximizes the probability of being within the target dosing interval. Therefore, the model’s recommendation would be to stay at  $1 \times 10^{12}$  vp, which is associated with the highest target dosing probability of 0.418 compared with that of  $3 \times 10^{10}$  vp (0.068) and  $3 \times 10^{11}$  vp (0.254).

Similarly (although not shown on Figure 2), according to the rules specified above, the model could possibly recommend to de-escalate to a lower dose level than the current treated dose level, escalate to the next dose level, or even recommend to stop and identify a new dose level lower than  $3 \times 10^{10}$  vp, the lowest pre-specified dose level. Please refer to the description of [Figure 1](#) for details on how to specify the new dose levels.

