3) A minimum number of participants (ie, 6) was treated at this dose level.

The final recommended dose (RD) for BMS-986277 monotherapy will be based on the recommendations from the BLRM and overall clinical assessment of all available safety, PK, pharmacodynamic, and efficacy data. Lower doses of BMS-986277 may be tested if none of the planned doses are found to be tolerable as monotherapy. Such decisions will be made after discussion and agreement between the investigators and the BMS Medical Monitor (or designee).

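### Part 1 stopping rule 4 declares the BLRM-RD without condition 2 of the BLRM-RD definition (the 35% overdose cap and the largest target probability): a minor rule inconsistency

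*Protocol*

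**What the plan says.** Protocol Appendix 9, Section 2.1 lists four general stopping rules for monotherapy escalation. The fourth needs two things at the current dose: 6 treated, and a chance above 50% that it is the target dose. If both hold, "then the model will suggest to stop and declare the current dose level to be the BLRM-recommended dose (BLRM-RD".

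The BLRM-RD definition follows at once and has three numbered conditions:

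1. Posterior probability above 50% that the DLT rate lies in 16% to <33%.
2. "This probability needs to be the largest among the dose levels that satisfy the EWOC condition", where the EWOC condition is a probability of at most 35% that the DLT rate is 33% or more.
3. At least 6 treated at the dose.

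Protocol 10.1.1.1 and SAP 6.1 repeat all three. (Another sentence of SAP 6.1 puts the cap at 25%. I use 35%, the figure in its condition 2 and in the protocol.)

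Elsewhere the cap is worded for choosing the next dose. Section 2.1 says "Only the candidate doses will be considered for the next cohort", and the text on Figure 2 says "When recommending the next dose level, the model will first exclude doses that are intolerable". The second stopping rule uses the EWOC criterion only when all doses are intolerable.

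**The concern.** Rule 4 restates conditions 1 and 3 and leaves out condition 2, with both its parts. It does not refer to the definition below it. It is the only stopping rule that declares a dose.

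The omitted parts are not implied by the others. The probabilities of under-dosing, target and overdose sum to 1, so a target probability above 0.50 and an overdose probability above 0.35 can hold together whenever under-dosing is below 0.15. Coded or applied as printed, rule 4 could end Part 1 on a dose above the cap, or on a higher dose when a lower one meets all three conditions.

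Determining the recommended dose is a primary objective. The Part 1 result feeds the planned Part 2 dose levels, and Part 3 Cohort 3 receives the Part 1 recommended dose itself.

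**Working it through.** **Inputs (Protocol Appendix 9).** Section 2.2: prior means (-0.959, 0.884), variances (1.010, 1.537), correlation 0.055; cohorts of 3; at most 24 in total and 12 per dose; reference dose 3x10^12 vp. Section 2.3: no dose skipping. I read 6 subjects as at least 6, and the chance of being the target dose as P(16% <= DLT rate < 33%).

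**Model.** logit p(dose) = log(alpha) + beta x log(dose / 3x10^12), integrated numerically on a grid.

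**Reproducing the plan's figures.** For the Figure 2 example (0/3 at 3x10^10, 1/3 at 3x10^11):

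| Quantity | Printed | Recomputed |
|---|---|---|
| P(target), 3x10^10 | 0.068 | 0.068 |
| P(target), 3x10^11 | 0.254 | 0.257 |
| P(target), 1x10^12 | 0.418 | 0.415 |
| P(overdose), 3x10^12 | 0.579 | 0.561 |

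The largest gap is 1.8 points. Section 3.1 gives a second check. It says that after 0/3 at 3x10^10 the model itself would go to 3x10^12. My P(overdose) there is 0.392, which the cap excludes. Taken at face value, that is a gap of at least 0.392 - 0.35 = 4.2 points, in the opposite direction. The figures below are therefore approximate.

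**Example A: the cap.** 0/3 at each of the three lower doses, then 0/3, 1/3, 0/3, 3/3 at 3x10^12.

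- No earlier stop occurs: P(target) at 3x10^12 is about 0.49 at 1/6 and 0.44 at 1/9.
- At 4/12: P(under) 0.07, P(target) 0.52, P(overdose) 0.41.
- Rule 4 declares 3x10^12. The definition rejects it, since 0.41 > 0.35. It names no other dose, because P(target) at the lower doses is 0.05 or less.

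**Example B: the largest-probability part.** 1/3 at 3x10^10; 1/3 then 0/3 at 3x10^11; 0/3 then 2/3 at 1x10^12.

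| Dose | DLT/n | P(target) | P(overdose) |
|---|---|---|---|
| 3x10^11 | 1/6 | 0.571 | 0.116 |
| 1x10^12 (current) | 2/6 | 0.547 | 0.364 |

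Rule 4 declares 1x10^12. The definition names 3x10^11, which meets all three conditions. The cap excess at 1x10^12 is only 1.4 points, within model error, so this example rests on the lead of 0.571 - 0.547 = 2.4 points.

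**Frequency.** All Part 1 paths were enumerated with rule 4 applied alone, on a 301 x 301 grid. The table gives the percentage of trials in which the declared dose fails condition 2.

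| Scenario (Table 3) | Above cap | Within cap, not largest | Total |
|---|---|---|---|
| By prior | 3.03 | 0.00 | 3.0 |
| Flatter | 1.57 | 1.89 | 3.5 |
| Narrow window | 1.73 | 0.00 | 1.7 |
| All low | 0.56 | 0.00 | 0.6 |
| All within | 2.16 | 2.67 | 4.8 |

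Two near-threshold states carry much of this:

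- **3/9 at 3x10^12 after clean lower doses.** P(target) is 0.502 to 0.506 depending on the grid. It contributes 2.79, 1.07, 1.58, 0.53 and 0.37 points in the order of the table.
- **1/3, 0/3, 0/3, 2/6.** The two top doses tie at 0.540 on this grid. On a finer grid the current dose leads slightly, so there is no conflict. It contributes 1.44 (flatter) and 1.71 (all within).

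Without both states:

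- By prior: 3.03 - 2.79 = 0.24%.
- Flatter: 3.46 - 1.44 - 1.07 = 0.95%.
- Narrow window: 1.73 - 1.58 = 0.15%.
- All low: 0.56 - 0.53 = 0.03%.
- All within: 4.83 - 1.71 - 0.37 = 2.75%.

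A separate enumeration on a finer grid gave totals of 3.0, 1.9, 1.7, 0.6 and 2.8%. The tie explains most of the difference from the table.

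**The case against.** The strongest reply is that the documents already settle the reading. Rule 4 says the model suggests declaring a BLRM-RD, and that term is defined immediately below, again in Protocol 10.1.1.1, and again in SAP 6.1, which requires that "A minimum number of participants (ie, 6) was treated at this dose level" alongside the other two conditions. A dose that fails the definition is not a BLRM-RD. Section 2.2 also lists the 35% limit under a lead-in that covers "the stopping rules used to identify the BLRM-RD, and other simulation parameters are defined as". Nor does the model have the last word: "The final recommended dose will be based on the BLRM-RD and overall clinical assessment". Part 2 then starts one level below the recommended dose.

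Most of this stands. It makes the shorthand reading plausible and keeps the point minor. A reader might go further and infer that Part 1 has no overdose control when a dose is declared, or that the Table 3 simulations ran without it. The documents support neither. The cap is in the definition and in the choice of each next dose, and Section 2.2 lists it among the simulation parameters.

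The numerical objection also has force. Example A clears the 50% trigger by about 2 points and Example B leads by 2.4. Both margins are smaller than the 4.2-point gap implied by Section 3.1. Example A's excess over the cap, about 6 points, is larger. Reaching 3x10^12 after three clean cohorts depends on an overdose probability of about 0.35, although Section 3.1 itself says 0/3 at 1x10^12 escalates.

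Using the 50/50 mixture of Section 1.2.3 directly would not support Example B. After 1/3 at 3x10^10 it gives P(overdose) of 0.468 at 3x10^11, so escalation is barred and the state cannot be reached. It also misses the printed Figure 2 values (target 0.177, 0.334, 0.355 against 0.068, 0.254, 0.418).

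What remains does not depend on the decimals. Two printed rules for the same declaration differ, and the shorter does not imply the longer.

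**Conclusion.** The point holds as a minor rule inconsistency. Stopping rule 4 omits one numbered condition, with two parts, from the BLRM-RD definition. Under the prior in Section 2.2, applying it alone can declare a dose that the definition rejects. The size is roughly 0 to 5% of trials depending on scenario, falling to about 0 to 3% when the two near-threshold states are set aside.

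This rests on rule 4 being used without the definition, on the single bivariate normal prior, on cohorts of exactly 3 without skipping, and on a reconstruction that matches the printed values only to within a few points. The final dose also depends on clinical judgement, so a changed BLRM-RD need not change the recommended dose.

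**What to change.** End stopping rule 4 with: *and all BLRM-RD conditions below (including the 35% overdose limit and the largest target probability) are met; otherwise continue under the escalation rule.* A new stopping trigger for doses other than the current one is not needed to cure this defect.

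The cost is one clause in the appendix. If the shorthand reading was intended, nothing changes. Otherwise slightly fewer trials may end with a declared BLRM-RD. Example A would pass to clinical assessment without one, while Example B would go back to 3x10^11 for its next cohort. The limit of 24 is unchanged. As a crude bound on sample size, at most 4.8% of trials are affected and none can add more than 24 - 6 = 18 participants, so the average rises by less than 0.048 x 18 = 0.9.

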### **BLRM-RD:**

The BLRM-RD is the dose that satisfies the following 3 conditions:

- 1) The empirical posterior probability that the ‘DLT rate of 16% to  $< 33\%$ ’ is greater than 50%,
- 2) This probability needs to be the largest among the dose levels that satisfy the EWOC condition (ie, the probability that ‘DLT rate  $\geq 33\%$ ’ must be no greater than 35%);
- 3) Minimum number of participants (ie, 6), were treated at this dose level.

### **Final Recommended Dose:**

The final recommended dose will be based on the BLRM-RD and overall clinical assessment of all available safety, PK/pharmacodynamic, and efficacy data. Lower doses of BMS-986277 may be tested if none of the planned doses are found to be tolerable. Such decisions will be made after discussion and agreement between the investigators and the BMS Medical Monitor.

## **2.2 Simulation Parameters**

Simulation study was done for monotherapy dose escalation using various hypothetical scenarios. One thousand trial simulations were used for each scenario. All simulations were run using EAST 6.3.1® software BLRM module for BMS-986277 monotherapy. The number of participants to be

treated in each cohort in a specific dose level, the stopping rules used to identify the BLRM-RD, and other simulation parameters are defined as:

- Fixed cohort size: 3
- Probability of overdosing:  $\leq 35\%$
- Target probability of toxicity: 0.33, the upper boundary of the targeted toxicity interval
- Probability of achieving the target toxicity:  $> 50\%$
- Maximum number of participants treated: 24
- Prior specification on model parameters:
  - Mean:  $\log(\alpha_1) = -0.959$ ,  $\log(\beta_1) = 0.884$
  - Variance:  $\log(\alpha_1) = 1.010$ ,  $\log(\beta_1) = 1.537$
  - Correlation: 0.055
- Posterior sampling method: Metropolis Hastings
- Minimum number of participants treated at a given dose level in order to identify the BLRM-RD: 6
- Maximum number of participants at a dose: 12

The provisional dose levels for BMS-986277 monotherapy are  $3 \times 10^{10}$ ,  $3 \times 10^{11}$ ,  $1 \times 10^{12}$ , and  $3 \times 10^{12}$  vp, with  $3 \times 10^{12}$  as the reference dose (dose expected to have 30% DLT).

### **2.3 Operating Characteristics of BLRM for Monotherapy**

Several scenarios were investigated by selecting (1) dose-DLT relationship derived by the prior, (2) dose-DLT curve flatter than the one by the prior; (3) narrow safety window (this scenario reflects a left-ward shift of the enadenotucirev dose-DLT relationship), (4) all doses below the target toxicity (this scenario reflects the enadenotucirev dose-DLT relationship at the BMS-986277 doses), and (5) all doses within the target toxicity range. Ten thousand simulations per scenario were performed using EAST v6.3.1 BLRM which allows dose skipping. However, there will be no dose skipping in dose escalation during the study conduct.

[Redacted text block]

**Table 3: Simulation Results of BLRM for Monotherapy**

Scenario	BMS-986277 Dose	3x10 	3x10 	1x10 	3x10 	MTD not Selected (%)	Fitted Median MTD	Avg Toxicity Observed (%)	Avg # Pts
By prior	% DLT	0	0	3	28				
	% MTD	0.0	0.0	50.7	49.3	0.0	3.2x10 	11.0	18.3
	# Pts	3.0	3.0	9.5	6.7				
	# DLTs	0.0	0.0	0.3	1.9				
Flatter than the one by the prior	% DLT	5	10	15	25				
	% MTD	0.3	4.2	62.8	32.3	0.4	3.1x10 	16.0	16.4
	# Pts	3.1	4.7	9.0	6.7				
	# DLTs	0.2	0.5	1.4	1.7				
Narrow safety window	% DLT	0	2	5	50				
	% MTD	0.0	0.0	85.8	14.2	0.0	2.9x10 	13.9	18.2
	# Pts	3	3.4	11.3	4.6				
	# DLTs	0.0	0.1	0.6	2.3				
All low	% DLT	0	0	0	10				
	% MTD	0.0	0.0	11.0	89.0	0.0	3.6x10 	5.5	18.6
	# Pts	3.0	3.0	6.5	10.0				
	# DLTs	0.0	0.0	0.0	1.0				
All within	% DLT	16	21	27	32				
	% MTD	6.5	22.9	54.8	10.7	5.1	1.9x10 	25.5	14.5
	# Pts	3.8	5.5	8.0	5.4				
	# DLTs	0.6	1.1	2.2	1.8				

Note: Bolded numbers are doses with true target toxicity within the target toxicity interval [16%, 33%]

Note: % DLT, true DLT rate; % MTD, proportion of the dose selected as the MTD; # Pts, average number of pts given the dose was tried; # DLTs, average number of DLTs given the dose was tried; Fitted MTD: fitted MTD at 33% as the target toxicity rate; % toxicity observed, average proportion of DLTs given the doses were tried

Abbreviation: Avg = average; NA = not applicable; Pts = participants.

The average sample size was no more than approximately 18 participants. Most scenarios have a fitted median MTD that is close to the reference dose and the  $1 \times 10^{12}$  vp dose was chosen as the MTD most frequently in all scenarios except the all low scenario. These results demonstrate how the EWOC principle limits the risk of exposing participants from a toxic dose level, where only the all low would select  $3 \times 10^{12}$  vp as the MTD most frequently. The prior parameters derived from the enadenotucerv DLT data suggests the selected doses are all relatively safe, with the DLT rate at  $3 \times 10^{12}$  vp artificially increased to allow for the potential increase in DLT due to the mechanism of activating T cells. This results in the  $1 \times 10^{12}$  vp dose selected as the MTD approximately 50% of the time. If, however, emerging data suggests the  $1 \times 10^{12}$  vp dose is relatively safe, the model will still allow  $3 \times 10^{12}$  vp to be selected as the MTD and this occurs approximately 50% of the time as well. This nicely illustrates the EWOC principle. The model performs well in the flatter than prior and all within scenarios by correctly identifying the MTD within the target toxicity interval, [16%, 33%) about 95% of the time and performs adequately by the prior scenario. Overall, the scenarios illustrated above demonstrate that the model performs satisfactorily in the hypothetical scenarios investigated by correctly identifying the MTD while limiting participants from receiving excessive/unacceptable toxic dose levels.

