**3.1 Example of using the BLRM for BMS-986277 Monotherapy Dose Escalation**

[figure not shown]
According to safety consideration and clinical judgement, the dose level  $3 \times 10^{10}$  vp is recommended as the starting dose for BMS-986277 monotherapy. With the current BMS-986277 prior specified in the Section 1.2 and all available DLT information up to  $3 \times 10^{12}$  vp, a

corresponding decision tree illustrating various models' recommendations under all possible scenarios for the first two cohorts is provided in Figure 4.

Tracing a branch of the decision tree in Figure 4 illustrates the decision making process. Taking the left-most branch of the tree as an example, starting at  $3 \times 10^{10}$  vp, if there were 0 DLTs observed in the real clinical trial, the model would recommend to escalate to  $3 \times 10^{11}$  vp (the BLRM actually recommends escalating to the highest dose  $3 \times 10^{12}$  vp, but since this is a 100-fold increase of dose and dose skipping is not allowed, the dose level  $3 \times 10^{11}$  vp is selected), one level above the current treated dose level according to the escalation rules per protocol. Next, if there is 0 DLTs observed at  $3 \times 10^{11}$  vp, the model would recommend to escalate further to  $1 \times 10^{12}$  vp. At  $1 \times 10^{12}$  vp, there would be 3 potential decisions (0/3 escalate, 1/3 and 2/3 would stay, and 3/3 would de-escalate); this is not shown due to crowding the diagram.

During the actual clinical study, the tree would be narrowed or deepened based on actual DLTs observed. The clinical team will be able to leverage this decision tree to preview decisions at each interim monitoring step and to plan proactively.

**Figure 4: The BLRM Model Hypothetical Decision Tree for BMS-986277 Monotherapy during Dose Escalation (for the first 2 cohorts)**

Abbreviations: DE = de-escalation; E = escalation; S = stay.

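### Appendix 9 reports about 95% in-target selection for the 'flatter' scenario only by counting a dose with a printed 15% DLT rate, and Table 3 does not describe the escalation design that will be run

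*Protocol*

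**What the plan says.** Appendix 9 Section 2.1 sorts true DLT rates into three classes, including "0%, 16%) under-dosing" and "16%, 33%) targeted toxicity", with square brackets inclusive and round brackets exclusive. A dose may be given next only if its probability of excessive toxicity (33% or more) is at most 35%. Protocol Section 10.1.1.1 and Appendix 9 Section 2.1 define the BLRM-RD by three conditions: posterior probability of the target interval above 50%, the largest such probability among doses passing the overdose criterion, and at least 6 participants treated at the dose.

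Table 3 gives the simulation results. Its note says: "Bolded numbers are doses with true target toxicity within the target toxicity interval [16%, 33"%]. In the 'flatter' row, 1x10^12 and 3x10^12 vp are bolded. The text after the table says the model performs well in 'flatter' and 'all within' "by correctly identifying the MTD within the target toxicity interval, [16%, 33%) about 95% of the time", and concludes that performance is satisfactory overall.

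Section 2.3 says the simulations were run "using EAST v6.3.1 BLRM which allows dose skipping. However, there will be no dose skipping in dose escalation during the study conduct". Section 3.1 says that after 0/3 DLTs at 3x10^10 vp "the BLRM actually recommends escalating to the highest dose", and that the no-skipping rule is what holds the next cohort at 3x10^11 vp.

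**The concern.** The printed 'flatter' rates are 5, 10, 15 and 25%. Only the last lies in the target interval, yet the text credits the model with about 95% correct selection. These operating characteristics are the stated evidence that the escalation finds the right dose while limiting toxicity. If a headline figure rests on counting an under-dosing level as a success, and the table comes from a rule set the trial will not use, the reader does not know how the actual design behaves. The gap matters most when the drug is well tolerated: the model may then often fail to name a BLRM-RD, and Table 3 gives no hint of it.

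**Working it through.** **1. The 95% figure.** Inputs are the Table 3 selection percentages.

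- 'All within' (true rates 16, 21, 27, 32%): 6.5 + 22.9 + 54.8 + 10.7 = 94.9%. All four doses are in [16%, 33%), so the claim holds.
- 'Flatter' (true rates 5, 10, 15, 25%): the row reads "0.3 4.2 62.8 32.3 0.4", the last entry being no selection. The stated figure is reproduced by 62.8 + 32.3 = 95.1%, which needs the 15% dose.
- With 16% ≤ rate < 33% applied as printed: 32.3% in target; 0.3 + 4.2 + 62.8 = 67.3% under-dosing; 0.4% none.

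Could 15 be a misprint for 16? The row reports 1.4 DLTs among 9.0 participants at that dose: 1.4/9.0 = 15.6%. Allowing for rounding, the range is 1.35/9.05 = 14.9% to 1.45/8.95 = 16.2%. Both values fit.

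**2. The prior and the Section 3.1 statement.** Appendix 9 Section 2.2 gives log(α) mean -0.959 and variance 1.010 (SD 1.005), log(β) mean 0.884 and variance 1.537 (SD 1.240), correlation 0.055 and reference dose 3x10^12 vp. I assume the usual form logit p(d) = log(α) + β·log(d/reference).

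At the reference dose p depends only on α. Before any data, P(p ≥ 0.33) = P(log α ≥ logit 0.33) = 1 − Φ((−0.708 + 0.959)/1.005) = 1 − Φ(0.250) = 0.40. Updating numerically for 0/3 at 3x10^10 vp gives about 0.39, above the 35% cap. Using the 50/50 mixture of the two Table 2 components instead of the single normal gives 0.38, and the MAP component alone 0.36. On any of these, 3x10^12 vp is not a candidate dose.

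As a check on the model form, I used the worked example in Appendix 9 Section 3 (0/3, then 1/3 at 3x10^11 vp). The protocol reports overdose probability 0.579 at 3x10^12 vp and target probabilities 0.068, 0.254 and 0.418 at the three lower doses. The same calculation gives about 0.56, and 0.068, 0.257 and 0.415.

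**3. The 'all low' row.** True rates are 0, 0, 0 and 10%, so no dose is in target, yet 11.0% + 89.0% = 100% of trials select an MTD. With 0/3 at each lower dose, the posterior probability of the target interval at 3x10^12 vp is:

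- after 0/6: about 0.32
- after 1/6: about 0.49
- after 1/12: about 0.36

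All are below 50%. Table 3's own averages at that dose, 10.0 participants and 1.0 DLT, lie between the last two cases. Condition 1 can be met by chance: 2/12 gives about 0.54. It is not met by the typical 'all low' trial.

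**4. Illustrative re-simulation.** Settings were no skipping, the 35% cap, all three BLRM-RD conditions, cohorts of 3, and maxima of 12 per dose and 24 in total. The share of trials ending with no qualifying dose was roughly 85% (by prior), 50% (flatter), 93% (narrow), 86% (all low) and 21% (all within). A separate run, which forced a selection at the sample-size limits, gave these average sample sizes:

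| Scenario | Table 3 | Skipping | No skipping |
|---|---|---|---|
| By prior | 18.3 | 18.2 | 21.2 |
| Flatter | 16.4 | 16.1 | 18.1 |
| Narrow | 18.2 | 17.5 | 20.4 |
| All low | 18.6 | 20.0 | 23.0 |
| All within | 14.5 | 14.4 | 14.8 |

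That run did not reproduce Table 3's selection percentages (flatter, top dose, skipping allowed: 15.8% against 32.3%), so its selection rule differs from the vendor's.

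**The case against.** Several points on the other side are fair.

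- The discrepancy is one percentage point, and a misprinted rate would leave the 95% intact. That stands: the documents show that three entries conflict, not which one is wrong.
- The skipping mismatch is disclosed in Section 2.3, and the no-skipping rule is repeated in Sections 3 and 3.1. That stands too, but disclosure does not supply the missing operating characteristics.
- Table 3 reports selection of an MTD, with the fitted MTD set at 33%. It does not claim to count trials that meet the BLRM-RD definition, and a redacted block before the table may state the selection rule. So the re-simulated shares and the table's column for no MTD selected are not the same quantity. Against this, Section 2.2 lists the 50% target probability, the 35% cap and the minimum of 6 among the simulation's own settings, so a reader will take the table as evidence about the BLRM-RD.
- The re-simulated shares depend on coding. With 0/3 at each of the three lower doses, the overdose probability at 3x10^12 vp is about 0.35, right at the cap, and small numerical differences decide whether escalation proceeds.

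Two stronger readings are tempting, and the documents do not support them. A reader might infer that the real design picks a sub-target dose in most 'flatter' trials. The 67.3% comes from a simulation with skipping; with about half of 'flatter' trials having no qualifying dose under the stated rules, at most about half could select any dose. A reader might also infer that a missing BLRM-RD leaves Part 2 without a dose. Protocol Section 10.1.1.1 and Appendix 9 Section 2.1 rest the final recommended dose on clinical assessment of all data as well as the model, and Section 10.1.1.2 starts Part 2 relative to that dose.

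**Conclusion.** The point holds in limited form. On the protocol's own numbers, 'about 95%' is correct for 'all within' (94.9%) and inconsistent with the printed 'flatter' rates, for which Table 3 gives 32.3% in target. That 32.3% is a table entry with skipping allowed; it is not the operating characteristic of the trial's design, which the documents do not report.

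The Section 3.1 recommendation conflicts with the stated prior and cap (about 0.39 against 0.35), assuming the usual two-parameter form. SAP Section 6.1 also prints a 25% cap in one sentence and 35% in the BLRM-RD conditions; 0.39 exceeds both. The 'all low' row is hard to reconcile with condition 1. Confidence is high for the table reading and good for the posterior probabilities, which track the protocol's worked example. The re-simulated shares and sample sizes show direction only, but they put the statement of no more than approximately 18 expected participants in doubt for the no-skipping design.

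**What to change.** 1. Reconcile the 15% rate, its bolding and the 95% sentence. If 15% is correct, remove the bolding and report 32.3% for 'flatter', labelled as the skipping-allowed figure, keeping 94.9% for 'all within'. If 16% was simulated, correct the rate.
2. Rerun Table 3 without skipping, under the stated cap (with the SAP's two values reconciled) and all three BLRM-RD conditions. State the rule used when a sample-size limit is reached, and report the share of trials with no qualifying dose and the average sample size. Give one number of runs: Section 2.2 says 1,000 and Section 2.3 says 10,000.
3. Reconcile the Section 3.1 statement on the model's recommendation after 0/3 with the overdose cap.
4. Say in Section 10.1.1.1 that the model may name no BLRM-RD, and that the recommended dose then rests on the clinical assessment already provided for.

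The cost is appendix text and one simulation rerun. No dose or escalation rule needs to change for this, but the stated performance will probably look less favourable.
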